12 DATA MANAGEMENT, BIOLOGIC MATERIAL, MONITORING, SAE

12.1 Data entry, data monitoring, data storage, data confidentiality

The PEs collect data directly in two tablet-based applications: PEBrApp (patient management tool and data collection tool) and KoboToolbox (data collection tool, incorporated in PEBrApp). The PEBrApp is password-protected and only accessible to the peer-educator that is responsible for the participant. All data will be regularly uploaded into a password-protected database. Similarly, relevant data for the SMS intervention will be entered and stored in a separate encrypted and password-protected online database, that offers the possibility to send out SMS automatically and is connected to the district laboratory database containing the VL results (VL platform, www.lstowards909090.org/db). The VL platform data are stored on a dedicated server in a data center, which meets FINMA-RS 08/07 requirements, is ISO-27001-certified, encrypts data in-transit with SSL and all patient names at-rest using OpenSSL with AES-256-CTR cipher method. SMS are dispatched using the trusted third-party provider Twilio, certified with the Privacy Shield Framework. Access to all data collection tools and databases are strictly limited and regulated through personal user profiles.

Data for the follow-up period comes from routinely collected medical records at the health facilities, primarily from the patient file, if necessary also from patients health booklet (bukana), antenatal care register, postnatal care register, ART register, ART treatment card and file, TB treatment register, TB treatment card, pharmacy register/dispensing logs, and the viral load monitoring platform. All the above mentioned documents act as source documents. For additional information that is not part of these documents, data is taken specifically for the study and the two data collection tools act as source document.

Following an initial period of weekly quality review, a study data manager will monitor data quality and completeness on a bi-monthly/monthly basis. Queries about the data will be sent to the local team for follow-up and correction, as needed. Data integrity checks will be written into the data collection tools to limit the entry of incorrect data and ensure entry of data into required fields.

Apart from the informed consent form, the study documents and data collection tools will not contain any names but solely the study-ID or unique ART number. There will be one confidential electronic master list with the subject identification code and the names. The informed consent forms will be stored in a secure way in the headquarter of the study center (SolidarMed Office in Butha-Buthe, Lesotho) and the master list will be stored in an encrypted online cloud with password controlled access and only accessible for pre-defined study personnel. Participant files will be maintained in storage for a period of at least 10 years after completion of the study.

12.2 Management of biologic material

Additionally, collected standard-lab-ID-coded blood samples would be stored at -80°C at the laboratory of Butha-Buthe government hospital. All samples that are stored at Butha-Buthe Government Hospital Laboratory fall under the current biobanking regulation agreement ("Biobanking regulations, v2.0"), approved by the ethics committees in Switzerland and Lesotho, and under the attached Material Transfer Agreement, submitted together with this study protocol (see Appendix 18.4) for approval. Remaining sample material after analysis of the ART drug levels will be destroyed.

12.3 Monitoring and Data Safety Monitoring Board (DSMB)

At least one external monitoring visit will assess compliance with the approved trial protocol, accuracy of completed data entries, and the electronic dataset. The Principal Investigator agrees to allow inspectors from regulatory agencies to review records and will assist the inspectors in their duties, if requested.

The PEBRA study represents implementation research, safety profiles of all used drugs are well-known, and the intervention does not include any new drugs. We do not expect major adverse effects on patients' health from this intervention. Moreover, participants in the PEBRA model can opt to switch back or be referred to facility-based care at any time during the trial period. Therefore it is not planned to establish a DSMB. Nevertheless, a safety monitoring plan for (Serious) Adverse Events has been outlined (see chapter 12.4) before the trial start.

12.4 Adverse Events (AEs) and Serious Adverse Events (SAEs)

Prescription and use of ART will follow current national guidelines of Lesotho. All ART used in Lesotho have a well-established safety profile. The most frequent adverse events are summarized on page 54 of the Lesotho national guidelines on the use of antiretroviral therapy for HIV prevention and treatment, 5th edition, 2016³⁰ and on page 138 of the consolidated guidelines on the use of antiretroviral drugs for treating and preventing HIV infection of the WHO³¹. AE and SAE will be graded according to the Division of AIDS Table for Grading the Severity of Adult and Pediatric Adverse Events, Version 2.0., November 2014³² and managed according to study sites standard procedure following the national guidelines. SAEs are defined as follows: a) life-threatening event, b) hospitalization, c) persistent or significant disability or incapacity, d) congenital anomaly / birth defect, e) death. In case of SAEs, any study personnel must inform one of the study physicians within 72 hours of his/her awareness of the SAE. The study physicians must then inform the Principal Investigator within 24 hours of his/her awareness of the SAE. The Principal Investigator will inform the local ethics committee in Lesotho within 48 hours. The study physicians are responsible for all direct safety procedures among study participants. If a participant develops an AE of Grade 2 or higher at last study visit, he/she remains under observation by the study physicians until the AE is resolved or stabilized.

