4.3.5 Intervention clusters: PEBRA model

The participants in the intervention clusters are offered the PEBRA model. In the PEBRA model the ART visit/refill is coordinated by the PE, as much as feasible according to the participants' preferences. Thus, the preferences of each participant are captured at enrolment and after a strict schedule thereafter. The PE conducts the preference assessment using a tablet-based application, called PEBRAApp. The PEBRAApp will automatically alert the PE when the next preference assessment of each participant is due. The preference assessment interval is independent from the ART refill interval and can be performed via phone as well. Participants with a suppressed VL will get a preference assessment every 3 months and participants with unsuppressed VL a preference assessment every month. As a strict part of the preference assessment, the PE asks two psychosocial questions ("Is there anything you would like to share with me today?" / "How do you think you are doing today?") and for those patients with unsuppressed VL an additional third question ("Do you have a safe environment to take your medication?").

The preference assessment works as a two-step approach: First, the participant will be asked his/her preference regarding different domains of DSD (see below) and this will be entered into the PEBRAApp. Secondly, the chosen preferences are assessed regarding feasibility with specific questions, as not all preference options are available to everyone all the time, e.g. no nearby Village Health Worker (VHW) available who could dispense ART, or no Community Youth Club (CYC) established in the participants' community, or home-delivery by PE not feasible.

The preference assessment entails the following three domains of DSD:

- 1) ART Refill
- 2) SMS notifications
- 3) Support

For each domain, the following options can be chosen:

- 1) ART Refill (one option possible):
 - a. At the clinic
 - b. Village Health Worker (VHW) in the community
 - c. Home-delivery by the PE
 - d. Through a Community Adherence Club (CAC)
 - e. Through a Treatment Buddy
- 2) SMS notifications (several options possible):
 - a. Adherence reminder: Frequency (to be chosen) and pre-defined message (to be chosen)
 - b. Refill visit reminder: Frequency (to be chosen) and pre-defined message (to be chosen)
 - c. VL-triggered message after blood draw as soon as VL result is available: pre-defined message for "unsuppressed" and "suppressed" (to be chosen)

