4.3.6 Control clusters: Standard of Care

Participants in the control clusters are offered standard of care: ART visit/refill is coordinated by the nurse, is mostly clinic-based and not specifically adapted to youth. Currently the Ministry of Health is piloting an SMS notification system that alerts patients once their VL result is out and entered into the LIS (Laboratory Information System). Thus, the standard of care at the health facilities in our study districts nowadays entails several options, however not all option are available at all health facilities:

- 1) ART Refill:
 - a. Nurse at the clinic
 - b. Through a Community Adherence Club
 - c. Through a Treatment Buddy
- 2) SMS notifications:
 - a. VL-triggered message: "Your laboratory result is out. Please come to the health facility to collect it"
- 3) Support:

- a. Nurse at the clinic
- b. Community Youth Club
- c. Saturday Clinic Club

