5.2 Secondary endpoints

- a) Adherence to ART at 3 months (range 2.5 – 3.5), 6 months (range 5 – 8) and 12 months (range 9 – 15) after enrolment
 - i. *Assessed by 4 different setting- and age-validated ART adherence questions²⁰⁻²²:*
 - a. *pill count: change in percentage*
 - b. *"When was the last time you missed any medications?" [i) past week, ii) 1-2 weeks ago, iii) 3-4 weeks ago, iv) never]: Dichotomous outcome missed doses vs. no missed doses in the past month*
 - c. *"ART missed at two or more consecutive days within last month?" ("drug holiday" question)*
 - d. *"How would you rate your adherence over the last month" [i) very poor, ii) poor, iii) fair, iv) good, v) very good, vi) excellent]: Dichotomous outcome adherent vs non-adherent (anything less than 'excellent')*
- b) Quality of Life (QoL) at 6 months (range 5 – 8) and 12 months (range 9 – 15) after enrolment
 - i. *Assessed by WHO QoL in PLHIV: WHO HIV QoL questionnaire (whoqol_hiv_bref questionnaire with 31 five-point Likert Scale items with categorical outcome)²³⁻²⁵*
- c) Perceived quality of ART Care (QoC) / patient service satisfaction at 6 months (range 5 – 8) and 12 months (range 9 – 15) after enrolment
 - i. *Assessed by a setting-validated QoC and patient service satisfaction questionnaire (12 five-point Likert Scale items with categorical outcome)²⁶ by an external data collector, not the PE*

- d) Engagement in care at 6 months, defined as the proportion of participants engaged in care 6 months (range 5 – 8) after enrolment out of all participants enrolled
 - i. *Definition of “in care”: at least one ART visit in the defined window*
 - I. *Including participants who transferred out to any other health facility with known outcome (documented proof of follow-up visit or laboratory test)*
 - II. *Excluding participants who died (all-cause), were lost to follow-up (LTFU), or were known defaulters/refusers, i.e. were more than 2 months late for ART refill with a reason available (e.g. currently no money for clinic-visit, busy working in South Africa, etc.)*
- e) Alternative viral suppression at 12 months, defined as the proportion of participants with a documented VL <1000 copies/mL 12 months (range 9 – 15) after enrolment out of all participants enrolled
 - i. *Rational for alternative VL suppression definition at 1000 copies/mL: According to the currently used Lesotho national guidelines, an unsuppressed VL is defined as a 1000 copies/mL or more*

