5.3 Safety Endpoint

We specifically assess the safety of our PEBRA model, defined as the proportion of participants experiencing a Serious Adverse Events (SAE) within 12 months after enrolment out of all participants enrolled. See chapter [12.4](#) for a detailed description of SAEs.

TABLE 1. Summary of PEBRA study endpoints

endpoints	Following enrolment		
	At 3 months (range: 2-5 – 3.5)	At 6 months (range: 5-8)	At 12 months (range: 9-15)
In care with documented viral suppression <20 copies/ml			Primary
Adherence to ART	Secondary	Secondary	Secondary
QoL	Secondary	Secondary	Secondary
QoC	Secondary	Secondary	Secondary
In care with documented viral suppression <1000 copies/ml			Secondary
Engagement in care		Secondary	Secondary
All-cause mortality		Secondary	Secondary
LTFU		Secondary	Secondary
Transfer out		Secondary	Secondary
SAE			Safety

Note: we consider 1 month = 30 days

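### The 12-month SAE endpoint has no ascertainment method common to both arms, so SAE proportions by arm are open to differential detection of uncertain direction

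*Combined protocol and SAP*

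**What the plan says.** Section 5.3 (Safety Endpoint) sets out to assess the safety of the PEBRA model, "defined as the proportion of participants experiencing a Serious Adverse Events (SAE) within 12 months after enrolment out of all participants enrolled". Table 1 lists it as the safety endpoint. Neither place says where, when or by what question SAEs are to be found.

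Section 12.4 defines SAEs as "a) life-threatening event, b) hospitalization, c) persistent or significant disability or incapacity, d) congenital anomaly / birth defect, e) death". Its reporting chain begins when someone on the study hears of the event: "any study personnel must inform one of the study physicians within 72 hours of his/her awareness of the SAE". Section 12.3 points to 12.4 as the safety monitoring plan and explains why no DSMB is planned.

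Contact differs by arm. In intervention clusters (4.3.5), "Participants with a suppressed VL will get a preference assessment every 3 months and participants with unsuppressed VL a preference assessment every month". The same section adds: "As a strict part of the preference assessment, the PE asks two psychosocial questions", one of which asks how the participant is doing. In control clusters (4.3.6), "ART visit/refill is coordinated by the nurse, is mostly clinic-based and not specifically adapted to youth", and no comparable contact is scheduled.

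Two things are common to both arms. Section 12.1 states: "Data for the follow-up period comes from routinely collected medical records at the health facilities". Section 5.2 schedules study assessments, beginning with "Adherence to ART at 3 months (range 2.5 – 3.5), 6 months" and then 12 months, with quality of life and quality of care at 6 and 12 months.

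**The concern.** A proportion of PEBRA participants with an SAE says little about the model's safety unless the control proportion stands beside it. That reading needs SAEs to be found about equally well in both arms, and nothing in the plan secures this. The trial is open label (4.3.8), the SAE pathway depends on someone hearing of the event, and the chance of hearing of it differs by design.

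Two errors become possible. An excess under PEBRA could be an artefact of closer contact, or a real excess could be dismissed as one. Conversely, if PEBRA moves refills away from the clinic and fewer events reach the records, a real excess could go unseen. In addition, the denominator is everyone enrolled, so a participant about whom nothing is known counts by default as free of SAEs.

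**Working it through.** The documents give no SAE rate, SAE power or SAE analysis, so there is no stated SAE figure to reproduce. The check sets the routes of detection side by side, counts contacts, and then shows what unequal capture would do under declared assumptions.

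**1. Routes by which an SAE can reach the endpoint**

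- *Awareness-triggered report (12.4):* both arms, but it depends on contact.
- *PE preference assessment with an open question (4.3.5):* intervention only.
- *Study assessments at 3, 6 and 12 months (5.2):* both arms. Their listed content is adherence, quality of life and quality of care, with no SAE item.
- *Routine records (12.1):* both arms, not assigned to SAEs. The list includes the patient's own booklet (bukana, used if necessary) and the antenatal and postnatal registers. It names no hospital admission or death register. Clusters are health centers (4.3.2), while hospitalization is an SAE criterion.
- *Mortality endpoint at 6 and 12 months (5.2 g):* both arms. It covers one of the five SAE criteria.

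**2. Scheduled contacts over 12 months**

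- Intervention, suppressed: 12/3 = 4 preference assessments.
- Intervention, unsuppressed: 12/1 = 12.
- Average at the 70% suppression in section 11.1: 0.7 × 4 + 0.3 × 12 = 6.4.
- Control: 0 preference assessments.
- Both arms: 3 study assessments.

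If study assessments coincide with preference assessments, the comparison is about 4 against 3 for suppressed participants and about 12 against 3 for unsuppressed ones. The gap is small for the first group and large for the second.

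**3. Effect of unequal capture (assumed values; none is in the documents)**

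Observed risk ratio = true risk ratio × (capture in intervention / capture in control).

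With equal true risk and 95% capture in intervention:

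- control capture 90%: 0.95/0.90 = 1.06
- control capture 70%: 0.95/0.70 = 1.36
- control capture 50%: 0.95/0.50 = 1.90

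With a true risk of 5% and 150 per arm, the expected number of participants with a detected SAE is 150 × 0.05 × 0.95 = 7.1 in intervention. In control it is 150 × 0.05 × 0.90 = 6.8, × 0.70 = 5.3, or × 0.50 = 3.8.

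Reverse case: with a true risk ratio of 1.5 and capture of 60% in intervention against 90% in control, the observed ratio is 1.5 × 0.60/0.90 = 1.0.

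**4. Chance of a spurious significant excess**

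The plan's design effect is reproduced: 1 + (15 − 1) × 0.05 = 1.70, giving an effective n of 150/1.7 = 88.2 per arm. For two-sided alpha 0.05, the chance of a significant excess under PEBRA is Φ[(p₁ − p₂ − 1.96 × SE₀)/SE₁], where p₁ and p₂ are the detected proportions, SE₀ uses the pooled proportion and SE₁ the separate ones. Over true risks of 3% to 15% and the three control capture rates above, it runs from about 3% (3% risk, 90% capture) to about 30% (15% risk, 50% capture). With few events, the harm is mainly to the estimate and its reading, and less to a test result.

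**5. Participants with no information**

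Section 5.2 h defines loss to follow-up partly by no information having been found. Section 5.3 keeps these participants in the denominator. If x of n enrolled have a known SAE and u have unknown status, the endpoint reports x/n, although the data only place the proportion between x/n and (x + u)/n. If u differs by arm, so does the understatement.

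**The case against.** The strongest reply is that the sentence in 12.4 sets a clock for expedited reporting and does not say how the 12-month endpoint is filled. A reader might infer that staff awareness is the only route into the endpoint, and the documents do not support that. The records in 12.1 apply to both arms, the booklet may show care received elsewhere, the antenatal and postnatal registers bear on birth defects, and deaths are counted separately in both arms. Controls are not without study contact either: a trained PE works in every cluster (4.3.4) and the 3-, 6- and 12-month assessments are common. The PE's questions are psychosocial and do not ask about SAEs. All of this stands and narrows the point. It does not close it, because no passage directs the records or the common assessments to SAEs.

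A reader might also infer that the bias must run against PEBRA. That is not supported. PE contact may raise detection, but refill through a village health worker, home delivery or a treatment buddy (4.3.5) may reduce clinic visits and with them record-based detection.

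Finally, sections 11.2 to 11.2.2 contain no SAE analysis, a detailed analysis plan is to follow separately (11.2), and the case report form is an attachment (18.3) that may hold SAE items. The last point cannot be checked here. The endpoint definition should still say how its events are found.

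**Conclusion.** The point holds in limited form. The protocol specifies no common SAE ascertainment for its safety endpoint, while scheduled contact that could bring SAEs to light differs by arm. SAE proportions by arm are therefore at risk of differential detection, and the sign of the bias cannot be known in advance. Participants with no information would by default count as SAE-free.

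It would be tempting to conclude that the between-arm SAE comparison is confounded and cannot be interpreted. That goes too far: no such comparison is written, several sources are shared by both arms, and the contact gap is small for suppressed participants.

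The size is illustrative only. Observed risk ratios of 1.06 to 1.90 with no true difference, or of 1.0 with a true ratio of 1.5, rest wholly on assumed capture rates. The conclusion that ascertainment is unspecified and contact unequal does not depend on them. It would weaken if the attached case report form already asks about SAEs at the same times in both arms. The change is worth making because it is cheap and uses contacts already planned.

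**What to change.** Amend sections 5.3 and 12.4 as follows:

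1. Add one fixed SAE question (hospital admission, life-threatening event, new disability, birth defect) to the 6- and 12-month assessments in both arms. It is preferably asked by the external data collector who already administers the quality-of-care questionnaire (5.2 c).
2. Do one record extraction for SAEs after month 12, with the same source list in both arms, including the bukana for every participant where it can be obtained.
3. Keep SAEs from any source in the endpoint. Show by arm how each was found (common method, or spontaneous PE or nurse report only), and give the comparison on common-method events as a sensitivity analysis. Limiting the main endpoint to common-method events would discard genuine SAEs.
4. Report the number per arm with unknown SAE status and do not treat them as SAE-free.
5. State in the separate analysis plan how the SAE endpoint will be summarised by arm.

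Expedited reporting in 12.4 is unaffected. The cost is a few added questions, some extraction work, and an amendment where section 13.1 requires one. One limit remains: the interview reaches mainly retained participants, so it may be answered more often in the arm with better retention. The unknown-status count makes that visible but does not remove it.

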13 ETHICAL CONSIDERATIONS

13.1 Research ethics approval / Informed consent / Amendments

This trial will be conducted in compliance with the protocol, International Conference on Harmonisation Good Clinical Practice E6 and the current version of the Declaration of Helsinki. Ethics approval will be sought from the National Health Research and Ethics Committee of Lesotho and the Ethikkomission Nordwest- und Zentralschweiz (EKNZ) in Switzerland and the trial will only commence once both committees have awarded approval. This is a cluster randomized health systems implementation research trial, thus its informed consent process is based on two fundamental principles that need to be balanced^{33,34}:

First, specific ethical requirements (e.g., informed consent, confidentiality, avoidance of harm) should be fulfilled. Second, a generally accepted claim is that a study being methodologically sound constitutes a necessary condition for its being ethically sound. Because only sound design can produce valid findings, methodological demands carry moral weight. In cluster-randomized trials, if participants would be aware of their cluster assignment and would know that there is another cluster arm with a different intervention, it would introduce the possibility of post-randomization selection bias and compromise the methodology. Some even argue that no individual informed consent should be obtained in a cluster-randomized trial in order to sustain a high-quality and sound methodology.³⁴ However, in our view we value individual consent higher and hence propose the following approach:

- Before cluster randomization, verbal consent from all health facility managers and the respective District Health Management Team will be obtained
- Before inclusion into PEBRA study we will obtain individual informed consent (for data collection and blood draw during follow-up), but using two different Informed Consent Forms (ICF) to keep the risk of selection bias as low as possible by concealing the allocation: One ICF for participants in PEBRA intervention clusters and one ICF for participants in PEBRA control clusters.

The trained PEs will obtain the individual informed consent from the participant before inclusion into PEBRA study. The investigator will explain to each participant the nature of the study, its purpose, the procedures involved, the expected duration, the potential risks and benefits and any discomfort it may entail. All participants will receive an information sheet and a consent form describing the study and providing sufficient information for participant to make an informed decision about their participation in the study before signing the consent form. Iliterate study participants will provide a thumb-print and a literate witness (independent to

the trial and chosen by the participant) will co-sign the form. The informed consent is provided in the local language, Sesotho, and the participant will receive a copy of the consent form. The participant has the right to withdraw consent at any time without giving reasons. In case of withdrawal, only data collected until the time of withdrawal will be used for research purposes (fully anonymized, identifier removed) and the participant will be managed according to standard of care.

This research includes adolescents and young people from the age of 15 years and older, a key group that is often neglected in research projects. One reason is that the consent process for people below 18 years is more complicated and usually requires a caregiver. This leads to decreased feasibility (e.g. most AYPLHIV do not come with their caregivers to the health facility) and to a negative bias in the study (e.g. caregivers not consenting although the AYPLHIV would agree). This is an operational research project, that does not test any new medication or experimental substances, but tries to tailor the services more according to the preferences of the AYPLHIV with the help of peer-educators and an electronic application. We strongly feel that it is feasible, justifiable and very important that these young people living with HIV give consent without parental consent, as it is being discussed in other research projects.³⁵⁻³⁹ Hence, we apply for a waiver of the parental consent for this specific research project.

Any modifications to the protocol which may impact on the conduct of the study, potential benefit to the patient or patient safety, including substantial changes of the study protocol, will require a formal amendment to the protocol and will be submitted to the Ethics Committee of Lesotho and the trial register (clinicaltrials.gov) will be updated accordingly.

